8.2.4 Pre-planned sensitivity or exploratory analyses

Sensitivity analyses will be performed according to the central pathology review. The efficacy endpoints will be analyzed in the populations that are defined as in 8.2.2 but considering the eligibility and the allocation to strata in the trial in function of the central pathology review assessment.

8.2.5 Prognostic factor analyses

Due to small patient numbers in each group, no prognostic factor analysis is planned.

8.2.6 Data recoding and display

Frequency tables will be tabulated (by treatment group or otherwise) for all categorical variables by the levels of the variables as they appear on the CRF (with %). Categories with a text field specification will be tabulated as categories and then supplemented by a listing with the following information for the patients fulfilling the condition for the specification (patient id, institution, treatment group, value of the item and text field contents).

Dates relating to events prior to entry will be presented as the delay in days (or weeks, months, or years) between the past event and the date of entry (date of registration – date of past event + 1) and presented using the median and range. For example, on the registration checklist, the date of last administration of prior treatment (or the date of first diagnosis of the cancer) will be presented as the time elapsed (in days, weeks, months or years, as appropriate) since the day of the last administration and the date of entry on study (date of registration – last administration/diagnosis +1).

Other delays (eg. re-treatment delays) are presented as continuous variables using the median and range.

Continuous variables for which a coding system exists (such as for laboratory data) will be recoded into categories (for adverse events, the grading scale specified in the protocol will be used).

Whenever no specific scale exists, lab data will be categorized based on the normal range: for example, below the lower normal limit (when appropriate), within the normal range, above the upper normal limit (UNL) and the degree to which it is above the UNL (for example > 2.5 x UNL, > 5 x UNL, > 10 x UNL). For laboratory data, the nadir is generally displayed. The nadir in a given cycle is the lowest laboratory value in that cycle; the overall nadir for a patient is the lowest laboratory value among all cycles.

Other continuous variables (for example age, dose ...) are presented using the median and range (minimum, maximum).

If appropriate, continuous data may also be presented in categories (for example, age may also be grouped in decades).

8.3 Interim analyses

No interim analysis is planned in this study.

8.4 End of study

End of study occurs when all of the following criteria have been satisfied:

1. Thirty days after all patients have stopped protocol treatment
2. The trial is mature for the analysis of the primary endpoint as defined in the protocol

3. The database has been fully cleaned and frozen for this analysis

9 Data monitoring

A Data and Safety Monitoring Board (DSMB) will monitor the recruitment, the reported adverse events and the data quality at least twice a year. Arising problems will be discussed with the Study Coordinator who will take appropriate measures. Relevant information (including relevant safety data) will be included in the study status reports serving as a basis of discussion during EORTC Group meetings. These reports will be made available to investigators participating to the study.

10 Translational research

In this phase II study of 64 patients exhibiting atypical (grade WHO II) or malignant (grade WHO III) meningiomas are intended to be included. The effect of high dose irradiation on the disease will be assessed. Every patient entering the study must be asked to accord with the translational research and to sign the translational research informed consent. Participation should be highly stimulated.

10.1 Objective of the translational study

The aim of the translational study is to correlate molecular characteristics of the tumour tissue with the natural history and with response to radiotherapy. To begin with there is the general importance of make inventory of the genetic aberrations and identify the damaged genetic pathways involved in the various tumors. To this aim, for the identification of crude chromosomal changes MLPA chips including probes for 1p, 22q and chromosome 11 will be used. . Secondly, the response to therapy of the various groups defined by their genetic aberrations will recorded and groups will be compared. For aberrations at the expression level array the use of CGH is anticipated.

10.2 Methods

This study is anticipating on tissue arrays, array CGH, RNA expression arrays (and possibly arrays at the protein expression level becoming available in due course of this long-term study) to be used upon availability.

10.3 Material needed

Paraffin-embedded tumor material should be available.

Fresh-frozen tumor samples for RNA and protein extraction are highly desirable.

Also 2 samples of peripheral blood (two 5 ml tubes with EDTA) are required (one before treatment and one after treatment) and must be stored as fresh frozen leucocytes (also immediately frozen EDTA full blood is acceptable).

Fresh-frozen tumor material should not be sent in before specific request by the PI of the translational research project. The appropriate addresses will follow.

E-mail: [contact]

The EORTC rules being in force for central pathology review will apply also for the fresh frozen material.

11 Investigator authorization procedure

Investigators will be authorized to register and randomize patients in this trial only once they have returned the following documents to the EORTC Data Center:

- ◆ The updated signed and dated curriculum vitae of the Principal Investigator.
- ◆ The (updated) list of normal ranges in the investigator's institution, signed and dated by the head of the laboratory. Please make sure normal ranges are provided also for those tests required by the protocol but not routinely done at the investigator's institution.
- ◆ A commitment statement / study acknowledgment form, stating that the investigator will fully comply with the protocol. This must include an estimate of yearly accrual and a statement on any conflict of interest that may arise due to trial participation.

NB: A signed conflict of interest disclosure form will be required only if a possible conflict is declared on the commitment form.

- ◆ A copy of the favorable opinion of the local or national (whichever is applicable) ethics committee mentioning the documents that were reviewed (including the version numbers and version dates for all documents). A list of all members of the ethics committee is also requested.
- ◆ A copy of the translated and adapted (according to all national requirements) Patient Information / Informed Consent sheet. Version numbers and dates must be clearly stated on each page.
- ◆ The signature log-list of the staff members with a sample of each authorized signature and the indication of the level of delegations. In case patients receive treatment at a satellite institution, i.e. outside the authorized institution, details on the satellite institution, including the CV of the local investigator, normal lab ranges and the approval of an ethics committee will have to be transmitted to the EORTC Data Center. **Please keep in mind that all communication is done ONLY between the primary institution and the EORTC Data Center.**
- ◆ The full name, address, phone numbers and e-mail address of the local pharmacist who will be responsible for the trial medication (for any trial where the drug will be provided).
- ◆ The accreditation letter for the laboratory (if available for a center and/or required by national law).

The center specific list of required documents will be included in the protocol activation package, with proper instructions as required by this protocol, your group and / or the applicable national law.

The new investigator will be added to the "authorization list", and will be allowed to randomize patients in the trial once

- ◆ all the above mentioned documents are available at the EORTC Data Center.
- ◆ all applicable national legal and regulatory requirements are fulfilled.

Patient registration from centers not (yet) included on the authorization list will not be accepted.

12 Patient registration procedure

Patient registration will only be accepted from authorized investigators (see "Authorization procedure").

A patient can be registered after verification of eligibility directly on the EORTC Data Center computer, 24 hours a day, 7 days a week, through the INTERNET network. To access the interactive registration/randomization program, the investigator needs a username and a password (that can be interactively requested: <http://www.eortc.be/random>).

Alternatively registration can be done by telephone to the EORTC Data Center from 9.00 am to 5.00 pm (Belgian local time) from Monday through Friday. The phone registration is not available on the official bank holiday of Belgium. A list of these dates will be available on our web site and updated yearly.

This must be done **before the start of the protocol treatment.**

[contact]

Internet: <http://www.eortc.be/random>

A patient who has not been registered before the first treatment administration will not be accepted for the study at a later date.

An exhaustive list of questions to be answered during the registration/randomization procedure is included in the registration check-list, which is part of the case report forms. This check-list should be completed by the responsible investigator before the patient is registered.

Standard questions

- ◆ institution number ?
- ◆ protocol number ?
- ◆ step number: 1
- ◆ name of the responsible investigator ?
- ◆ patient's code (maximum 4 letters) ?
- ◆ patient's chart number (if available) ?
- ◆ patient's birth date (day/month/year) ?

Group affiliation

- ◆ primary group affiliation ?
- ◆ secondary group affiliation ?

Protocol specific questions

- ◆ eligibility criteria ?
 - all eligibility criteria will be checked;
 - actual values of the eligibility parameters will be requested when applicable
- ◆ date of written informed consent ?
- ◆ date foreseen for protocol treatment start ?

At the end of the procedure, a patient sequential identification number will be allocated to the patients. This number has to be recorded on the registration check-list, along with the date of registration. The completed check-list must be signed by the responsible investigator and returned

to the data center with the initial data of the patient. The sequential identification number attributed to the patient at the end of the registration procedure identifies the patient and must be reported on all case report forms.

13 Forms and procedures for collecting data

13.1 Case report forms and schedule for completion

Data will be reported on the **EORTC forms** and sent to:

EORTC Radiotherapy Group Data Manager

[name]

EORTC Data Center

[name]

[name]

Case report forms must be completed according to the following schedule:

A. Before the treatment starts:

- ◆ the patient must be registered at the Data Center by INTERNET or by phone
- ◆ the registration check-list should be returned to the Data Center

The optimal way to work is to complete the registration check-list first and to register/randomize the patient as soon as it is completed. The date of registration and patient sequential identification number are then completed on the check-list, and this form can be sent to the Data Center.

B. The list of forms to be completed for this study and their submission schedule is appended to the set of case report forms

C. Upon occurrence of a Serious Adverse Event (SAE)

- ◆ SAEs occurring from the time a subject is registered until 30 days after last protocol treatment must be promptly reported.
- ◆ Any SAE occurring after the 30-days period and considered to be reasonably related to the investigational product or study participation, also have to be promptly notified
- ◆ All these events must be reported **by fax** to the **EORTC Pharmacovigilance Unit** on a Serious Adverse Event Form **within 24 hours** of the initial observation.
- ◆ A completed SAE-form must be returned to the Data Center within 10 calendar days of the initial observation of the Serious Adverse Event.

**ALL Forms must be dated and signed by the responsible investigator
or one of his/her authorized staff members**

13.2 Data Flow (Remote Data Capture)

The forms must be electronically completed according to the schedule defined in the CRF guidelines through the EORTC web based Remote Data Capture (RDC) system.

The list of staff members authorized to enter forms must be identified on the signature log and sent to the Data Center by the responsible investigator before the start of the study.

In all cases, it remains the responsibility of the investigator to check that data are entered on the database as soon as possible and that they are completely and correctly filled out.

On the data received, the EORTC Data Center will perform extensive consistency checks and issue queries in case of inconsistent data. Queries will be sent by email (PDF) or regular mail, and must be filled out on the printed paper. A copy should be kept on site, the original must be sent by regular mail to the EORTC Data Center.

The EORTC data manager will subsequently apply the corrections into the database.

If an investigator (or an authorized staff member) needs to modify a CRF after the form has been sent to the EORTC Data Center, he/she should use a Data Correction Sheet and sent it to the EORTC Data Center.

14 Reporting of Serious Adverse Events (SAE)

14.1 Definitions

AE: An **Adverse Event** is defined as any untoward medical occurrence in a patient or clinical trial subject administered a medicinal product and which not necessarily have a causal relationship with this treatment. An adverse event can therefore be any unfavorable and unintended signs (such as rash or enlarged liver), symptoms (such as nausea or chest pain), an abnormal laboratory finding (including blood tests, x-rays or scans) or a disease temporarily associated with the use of the protocol treatment, whether or not considered related to the investigational medicinal product.

AR: An **Adverse reaction of an investigational medicinal product** is any untoward and unintended responses to an investigational medicinal product related to any dose administered.

All adverse events judged by either the reporting investigator or the sponsor as having a reasonable causal relationship to a medicinal product qualify as adverse reactions. The expression reasonable causal relationship means to convey in general that there is evidence or argument to suggest a causal relationship.

UAR: An **Unexpected Adverse Reaction** is any adverse reaction, the nature, or severity of which is not consistent with the applicable product information (e.g. investigator's brochure for an unapproved investigational product or summary of product characteristics (SmPC) for an authorised product).

When the outcome of the adverse reaction is not consistent with the applicable product information this adverse reaction should be considered as unexpected.

Severity: The term “severe” is often used to describe the intensity (severity) of a specific event. This is not the same as “serious,” which is based on patient/event outcome or action criteria.

SAE: A **Serious Adverse Event** is defined as any undesirable experience occurring to a patient, whether or not considered related to the protocol treatment.

SAR: A Serious Adverse Event (SAE) which is considered related to the protocol treatment is defined as a **Serious Adverse Reaction**

An **Adverse Event** or **Adverse Reaction** which is considered as **serious**:

- ◆ results in death
- ◆ is life-threatening (i.e. an event in which the subject was at risk of death at the time of event; it does not refer to an event which hypothetically might have caused death if it were more severe)
- ◆ requires hospitalisation or prolongation of existing inpatients' hospitalisation
- ◆ results in persistent or significant disability or incapacity
- ◆ is a congenital anomaly or birth defect
- ◆ results in any other medically important condition (i.e. important adverse reactions that are not immediately life threatening or do not result in death or hospitalization but may jeopardize the patient or may require intervention to prevent one of the other outcomes listed above)

SUSAR: Suspected Unexpected Serious Adverse Reactions

14.2 Reporting procedure

14.2.1 Non- serious adverse events and/or non-serious adverse drug reactions

Adverse Events (AE) and /or Adverse Reactions (AR) must be recorded as indicated in the protocol.

14.2.2 Serious adverse events or serious adverse drug reactions

All Serious Adverse Events (SAE) occurring from the time a subject is registered until 30 days after last protocol treatment, must be reported to the EORTC Pharmacovigilance Unit within 24 hours. (Ref: <http://ctep.info.nih.gov/reporting/ctc.html>).

All SAEs that are simply signs and symptoms of the disease being studied do **NOT** need to be collected!

Examples of SAEs that do not need to be reported:

- ◆ Medical or surgical procedure (e.g., endoscopy, appendectomy); the condition that leads to the procedure is an AE
- ◆ Situations where an untoward medical occurrence did not occur (social and/or convenience admission to a hospital)
- ◆ Anticipated day-to-day fluctuations of pre-existing disease(s) or condition(s) present or detected at the start of the study that do not worsen
- ◆ The disease/disorder being studied, or expected progression, signs, or symptoms of the disease/disorder being studied, unless more severe than expected for the subject's condition
- ◆ A hospitalization which was planned before the patient consented for study participation and where admission did not take longer than anticipated.

Any SAE that occurs outside of the SAE detection period (after the 30-days period), considered to be reasonably related to the investigational product or study participation, have to be promptly notified to the EORTC Pharmacovigilance Unit.

This must be done by fax within 24 hours of the initial observation of the event. The principal investigator will decide if these events are related to the protocol treatment (i.e. unrelated, likely related, and not assessable) and the decision will be recorded on the Serious Adverse Event form, if necessary with the reasoning of the principal investigator.

The investigator is obligated to assess the relationship between investigational product and the occurrence of each AE/SAE. A "reasonable possibility" is meant to convey that there are facts/evidence or arguments to suggest a causal relationship, rather than a relationship cannot be ruled out. The investigator will use clinical judgement to determine the relationship. Alternative causes, such as natural history of the underlying diseases, concomitant therapy, other risk factors, and the temporal relationship of the event to the investigational product will be considered and investigated.

For the causality assessment, the following definitions must be used:

Relationship to the protocol treatment	Description
UNRELATED	There is no evidence of any causal relationship to the protocol treatment
LIKELY RELATED	There is (some) evidence to suggest a causal relationship to the protocol treatment and influence of other factors is unlikely or absent.
NOT ASSESSABLE	There is insufficient or incomplete evidence to make a clinical judgement of the causal relationship to the protocol treatment.

Details should be documented on the specified Serious Adverse Event Form.

PLEASE FAX THE REPORT TO:

EORTC Pharmacovigilance Unit:
[contact]

The EORTC Pharmacovigilance Unit will forward all Serious Adverse Event reports within 24 hours of receipt to all appropriate persons (**See Administrative chapter**).

To enable the EORTC Pharmacovigilance Unit to comply with regulatory reporting requirements, completed documentation of any reported serious adverse events or serious adverse reactions must be returned within 10 calendar days of the initial report. If the completed form is not received within this deadline, the Pharmacovigilance Unit will make a written request to the investigator.

It should be recognized that Serious Adverse Reactions (SAR) which have not been previously documented in the Investigators' Brochure, or which occur in a more severe form than anticipated (i.e. they are 'unexpected' by nature or severity), are subject to rapid reporting to the Regulatory Authorities.

ANY QUESTION CONCERNING SAE OR SAR REPORTING CAN BE DIRECTED TO:

EORTC Pharmacovigilance Unit
[contact]
[contact]
e-mail: [contact]

ALL FORMS MUST BE DATED AND SIGNED BY THE RESPONSIBLE INVESTIGATOR OR ONE OF HIS/HER AUTHORIZED STAFF MEMBERS.

15 Quality assurance

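### The mandatory three-category SAE causality scale has no place for an event with some evidence of a radiation cause and another plausible cause, and is stricter than the protocol's own test of relatedness

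*Protocol*

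**What the plan says.** Section 14.1 of the protocol defines an adverse reaction as an adverse event that the reporting investigator or the sponsor judges to have a reasonable causal relationship to treatment. It explains the term: "The expression reasonable causal relationship means to convey in general that there is evidence or argument to suggest a causal relationship". An SAE considered related to protocol treatment is a serious adverse reaction (SAR).

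Section 14.2.2 describes a reasonable possibility in nearly the same terms: it "is meant to convey that there are facts/evidence or arguments to suggest a causal relationship, rather than a relationship cannot be ruled out". Alternative causes are to be considered and investigated.

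The same section then introduces a table with the instruction "For the causality assessment, the following definitions must be used". The first row, *unrelated*, is for events where nothing points to treatment as a cause. The last row, *not assessable*, is for events where the information is too thin to reach a judgement. The only positive row, *likely related*, sits between them and sets two conditions: "There is (some) evidence to suggest a causal relationship to the protocol treatment and influence of other factors is unlikely or absent".

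Up to 30 days after the last treatment, SAEs are reported whatever their cause, apart from listed exceptions such as signs of the disease itself. After that, sections 13.1 and 14.2.2 make notification depend on relatedness. The wording in 14.2.2 is "Any SAE that occurs outside of the SAE detection period (after the 30-days period), considered to be reasonably related to the investigational product", extended to study participation. Unexpected SARs go rapidly to the regulatory authorities.

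**The concern.** The protocol uses two different tests for one judgement. Sections 14.1 and 14.2.2 ask only whether something points to a causal link. The table asks that too, but its single positive row adds a second condition about other factors. An event that passes the first test and fails the second is an adverse reaction by definition, yet has no category on the form.

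The combination is a realistic one in this trial. All patients have had surgery or a biopsy for a brain tumour, and Simpson stages 4-5 have residual tumour visible on MRI (section 3.2), so a second explanation for a neurological event will sometimes be credible. The harms described in the background include radionecrosis, optic neuropathy, pituitary insufficiency and hearing loss (sections 1.3 and 1.6.2). Several of these can appear well after day 30, when notification turns on relatedness.

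At stake are whether an SAE is classified as a SAR, whether an unexpected one goes quickly to the authorities, and whether an SAE after day 30 is notified at all.

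**Working it through.** No sample size, error rate or event count enters this point, and the protocol states no figure to reproduce. The check is whether the three categories cover every case and agree with section 14.1.

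**Step 1. Inputs.** The table rows use two dimensions: the evidence for a treatment cause (none, insufficient or incomplete, some) and the influence of other factors (unlikely or absent, plausible). That gives 3 × 2 = 6 combinations.

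**Step 2. Match each combination to the table, and to section 14.1 where evidence exists.**

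| Evidence for a treatment cause | Other factors | Category in 14.2.2 | Adverse reaction under 14.1? |
|---|---|---|---|
| None | Unlikely or absent | Unrelated | No |
| None | Plausible | Unrelated | No |
| Insufficient | Unlikely or absent | Not assessable | Not settled |
| Insufficient | Plausible | Not assessable | Not settled |
| Some | Unlikely or absent | Likely related | Yes |
| Some | Plausible | **None** | **Yes** |

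Five of the six combinations have a category and one does not. The last row cannot be *unrelated*, because evidence exists. It cannot be *likely related*, because another factor is plausible. On its wording it is not *not assessable* either: that row describes too little evidence, not evidence pointing to two causes.

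**Step 3. Compare the thresholds.** Neither section 14.1 nor the reasonable-possibility text requires other causes to be excluded. The *likely related* row does. The mandatory scale is therefore stricter than the definition it is meant to apply.

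**Step 4. Follow the uncovered case through the rules.**

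- *Up to day 30:* the SAE is reported regardless of cause, subject to the listed exceptions. The table can still affect whether it is called a SAR, and so whether rapid regulatory reporting applies.
- *After day 30:* notification requires that the event be considered reasonably related. An investigator who uses section 14.1 would notify. One who uses the table finds no positive category that fits.
- *If the site falls back on* not assessable: the protocol does not say whether that counts as reasonably related or as a SAR.

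**Step 5. Check the other route for late events.** Late CTCAE events are scored at every scheduled visit until progression with no causality condition (section 6.3.2). They are tabulated by worst grade, and time to first grade 3 or 4 late event is estimated (sections 8.2.1.3 and 8.2.3.3). None of this uses the causality table.

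**The case against.** The strongest reply is that the table does not decide whether a late SAE is notified. The trigger after day 30 is reasonable relatedness, which sections 14.1 and 14.2.2 describe without excluding other causes; the three categories are then recorded on a form that is already being sent. That reading is possible, and it is why non-notification is a risk and not a certainty. It does not remove the difficulty. Section 14.2.2 says the investigator decides relatedness by choosing among these categories, and an event that is notified can still be misclassified.

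A second reply is that past surgery or residual tumour does not by itself make their influence on a given event likely. That is right. How often the uncovered case would arise is unknown, and the protocol does not support saying that late toxicity would rarely qualify as *likely related*.

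A reader might go further and infer that late brain toxicity would never reach the sponsor or the DSMB. The protocol does not support this. Late events are collected irrespective of cause until progression, and under section 9 the DSMB monitors reported adverse events at least twice a year. That route is slower than the 24 hours set for an SAE, since visits are at 6 and 12 months and then yearly, and it ends at progression, after which only survival is followed.

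A reader might also apply the severe complication rate of one third in the 36-patient series (section 1.6.2) to this trial to count missed reports. That rate cannot serve. It comes from a series treated largely with accelerated hyperfractionation, and the same section gives 0% grade 3 and 0% grade 4 for patients not treated that way. It also describes severe events, which section 14.1 distinguishes from serious ones, and says nothing about reporting.

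**Conclusion.** The point stands as an internal contradiction with a limited safety consequence. The mandatory scale leaves one of six logical combinations without a category, that combination is an adverse reaction under section 14.1, and the status of *not assessable* is undefined. An SAE of this kind may be misclassified as not a SAR, or may go unnotified as an SAE after day 30.

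No number of affected patients can be given. The conclusion rests on reading the table as written and on its being mandatory; a site that applied section 14.1 directly would notify correctly. The late-toxicity tables, the progression-free survival endpoint, the sample size and the error rates are unaffected.

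The exemption for signs and symptoms of the disease might be read as part of the same fault. It is a separate rule that does not use the causality scale, and it carries its own limit for events more severe than expected. Tying it to progression on MRI would not work within the 30-day window: no MRI is requested at the 6-week visit, and the first follow-up MRI is at 6 months after entry.

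**What to change.** Reconcile sections 14.1 and 14.2.2 so that one test of relatedness applies throughout:

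1. Delete the second condition, on other factors, from *likely related*; or keep that row and add a *possibly related* category for some evidence together with another plausible cause.
2. State which categories, with *not assessable* named explicitly, count as reasonably related for notification after day 30 and as related for SAR classification.
3. Change the SAE form to match, and carry the same rule into section 13.1.

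The cost is a few lines of protocol text, an edit to the SAE form and some additional SAE reports. No analysis changes.
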